Chronic Pulmonary Aspergillosis (CPA)	TOC (Day 90 or EOT, whichever occurs first) (EOT, Day 90, Day 180, every 3 months while on Tx if beyond Day 180, 6-Week FU)	Global Response = Successful Overall CPA Response , defined as subjects who are judged to have shown improvement of the disease by clinical, radiological and mycological parameters and those that achieved stable disease after entering the study with a rapidly progressing condition.	Global Response (as defined) Clinical Response = defined as a decrease in the St. George's Respiratory Questionnaire (SGRQ) score by ≥ 4 points SGRQ outcomes will be categorized as follows: 
 Improvement: Decrease in SGRQ by ≥ 4 points Stability: Change in SGRQ between: increase by <4 to decrease by <4 Deterioration: Increase in SGRQ by ≥ 4 point Radiological Response will be assessed using chest CT scan and will be categorized as: 
 Radiological Improvement: $>30\%$ decrease in volume of fungus ball AND/OR 20% decrease in cavity wall thickening AND/OR 20% improvement in pleural thickening. Radiological Deterioration: $>30\%$ increase in volume of fungus ball AND/OR 20% increase in cavity wall thickening AND/OR 20% increase in pleural thickening. Subjects with measurements fulfilling any of the criteria for radiological deterioration will be classified as deteriorated, even if they also fulfil a criterion for improvement. Radiological Stability: No notable change in radiological image. Mycological Response = reduction in Aspergillus IgG by $\geq 20\%$ AND/OR negative sputum culture for Aspergillus

Fungal disease	Primary time point (Secondary time points)	Primary Outcome Definition	Secondary Outcome Definitions (disease-specific outcome definitions, if not previously defined) ^{a, c}

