
○ Efficacy Timepoints and Outcome Definitions for primary and secondary endpoints	
Primary Efficacy Timepoints changed as follows:
 
CMC: TOC (Day 84 or EOT, whichever comes first) CPA: TOC (Day 90 or EOT, whichever comes first) ABPA: TOC (Day 90 or EOT, whichever comes first)
 
Outcome definitions changed as follows:
 
○ EC and OPC Clinical Response (including radiological outcome if done as SOC)○ VVC Primary Outcome Definition: Global Response = Clinical Success Improvement, defined as at least 50% reduction from baseline in complete or partial resolution of signs and symptoms with total composite score not >1, without use of additional antifungal○ VVC Secondary Outcome Definition: Global Response (as defined) Clinical Response = Clinical Cure, defined as complete resolution of all signs and symptoms (VSS = 0) without use of additional antifungal (Reference FDA guidelines 2016); Resolved VVC infection (score <3) Mycological Response = mycological eradication for the baseline pathogen Symptom resolution at FU (clinical cure, resolved infection, clinical success) Responder outcome (Clinical Cure and mycological eradication) at TOC and FU 
EORTC-MSG table for General Criteria for Global Responses to Antifungal therapy (Table 17) – additions as follows:
 
○ Global Response - Success definition for step-down therapy added: For subjects who were enrolled for step-down therapy and who were asymptomatic at baseline: no new symptoms or signs suggestive of disease and no new positive cultures.○ Partial Response: Survival within a prespecified period of observation, improvement in attributable symptoms and signs of disease and radiological abnormalities, and evidence of clearance of cultures or reduction of fungal burden, and

Protocol Amendment 3	
Main affected Protocol Sections	Change and Rationale
	
no new positive cultures, as assessed by a quantitative and validated laboratory marker
 
○ Added a category “Not Evaluable”Not Evaluable – Outcome cannot be assessed due to missing data○ Added a statement: When the MSG_EORTC criteria is not fully applicable for a specific case, the DRC will adjudicate outcome based on acceptable criteria, per their judgement.
○ Survival	
Updated:
 
Survival status (collected as ACM) will be recorded at Day 30 for IC/Candidemia and at Day 42 for all.

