### **STATISTICAL ANALYSIS PLAN DOCUMENT HISTORY**

Version Number	Author	Date	Change
Draft		21Dec2022	Initial
Final 1.0		14Apr2023	NA

Version Number	Author	Date	Change
Final 1.1		8April2024	
Section 3.2 – Update definition of Per-Protocol Population to clarify major protocol violations.
 
Section 6.2.2 – Clarified that the missed dose information is located in the Missed Dose Log when calculating compliance.
 
Section 7 – Clarification around baseline enrollment categories and determination of the potential impact of protocol deviations on the efficacy-related outcomes.
 
Table 5 – Clarification around definitions used for Global, Clinical, and Mycological Response.
 
Section 7.1.1 – Clarification on TOC definition for CMC, CPA, and ABPA subjects. Addition of the Step-down baseline enrollment category determined by the PI.
 
Section 7.2 – Clarification around how survival status information was collected and how censoring was performed.
 
Table 7 – Addition of VVC specific endpoints to be consistent with the information in Table 5.
 
Section 7.2.3 – Clarification around mycological response definitions and alignment with protocol versions.
 
Section 8.2.1 – Clarification around how child-bearing potential information was collected.

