Chronic Pulmonary Aspergillosis (CPA)	TOC (Day 90 or EOT, whichever occurs first) (EOT, Day 90, Day 180, every 3 months while on Tx if beyond Day 180, 6-Week FU)	Global Response = Successful Overall CPA Response , defined as subjects who are judged to have shown improvement of the disease by clinical, radiological and mycological parameters and those that achieved stable disease after entering the study with a rapidly progressing condition.	Global Response (as defined) Clinical Response = defined as improvement or stability in the St. George's Respiratory Questionnaire (SGRQ) score. SGRQ outcomes will be categorized as follows: 
 
• Improvement: Decrease in SGRQ by <math>\geq 4</math> points
 
• Stability: Change in SGRQ between: increase by <math><4</math> to decrease by <math><4</math>
 
• Deterioration: Increase in SGRQ by <math>\geq 4</math> point
 
 Radiological Response will be assessed using chest CT scan and will be categorized as: 
 
• Radiological Improvement: <math>>30\%</math> decrease in volume of fungus ball AND/OR <math>20\%</math> decrease in cavity wall thickening AND/OR <math>20\%</math> improvement in pleural thickening.
 
• Radiological Deterioration: <math>>30\%</math> increase in volume of fungus ball AND/OR <math>20\%</math> increase in cavity wall thickening AND/OR <math>20\%</math> increase in pleural thickening. Subjects with measurements fulfilling any of the criteria for radiological deterioration will be classified as deteriorated, even if they also fulfil a criterion for improvement.
 
• Radiological Stability: No notable change in radiological image.
 
 Mycological Response = reduction in Aspergillus IgG by $\geq 20\%$ AND/OR negative sputum culture for Aspergillus

Fungal disease	Primary time point (Secondary time points)	Primary Outcome Definition	Secondary Outcome Definitions (disease-specific outcome definitions, if not previously defined) a, e

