## 7.1 Primary Endpoint

The primary efficacy objective is to evaluate the efficacy of ibrexafungerp in the treatment of severe fungal diseases by a Data Review Committee (DRC) at the primary timepoint for the fungal disease (as defined in [Table 5](#)). The primary efficacy endpoint of the study is the percentage of subjects who achieve Global Response (as defined in [Table 6](#)) at TOC (Day 17) for VVC, CMC (EOT or Day 84), CPA (EOT or Day 90) and ABPA (EOT or Day 90) (whichever comes first) and at EOT for all other diseases, as determined by the DRC. The analysis criteria will be based on EORTC-MSG Consensus Criteria for all diseases except ABPA, CPA and VVC.

Table 6 EORTC-MSG General Criteria for Global Responses to Antifungal Therapy with adaptations a and b

Global Response	Outcome Criteria
Success	Complete Response: Survival within the prespecified period of observation, resolution of all attributable symptoms and signs of disease and radiological abnormalities, and mycological evidence of eradication of disease a For subjects who were enrolled for step-down therapy and who were asymptomatic at baseline: no new symptoms or signs suggestive of disease and no new positive cultures.
	Partial Response: Survival within a prespecified period of observation, improvement in attributable symptoms and signs of disease and radiological abnormalities, and evidence of clearance of cultures or reduction of fungal burden, and no new positive cultures, as assessed by a quantitative and validated laboratory marker
Failure	Stable Response: Survival within a prespecified period of observation and minor or no improvement in fungal disease, but no evidence of progression, as determined on the basis of a composite of clinical, radiological and mycological criteria.
	Progression of Fungal Disease: Evidence of progressive fungal disease based on a composite of clinical, radiological and mycological criteria
	Death: Death during the prespecified period of evaluation, regardless of attribution
bNot Evaluable	Outcome cannot be assessed due to missing data

aDefinition added in Amendment 3 for subjects enrolled for step-down therapy and asymptomatic at baseline. DRC adjudications followed this definition for all subjects, PI adjudication followed this definition for subjects enrolled after Amendment 3.

bCategory added for non-evaluable subjects due to missing data

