**Clinical Response (all non-radiological clinical symptoms and physical findings):**

1. Resolution of all attributable clinical symptoms and physical findings (i.e., resolution of all clinical symptoms and physical findings of fungal disease present at Baseline and/or resolution of those that appeared at a subsequent visit)
2. Resolution of some attributable clinical symptoms and physical findings (i.e., resolution of some but not all clinical symptoms and/or physical findings of fungal disease present at Baseline and/or of those that appeared at a subsequent visit)
3. No resolution of any attributable clinical symptoms and physical findings and/or worsening (i.e., no resolution or worsening of any clinical symptoms and/or physical findings of fungal disease present at Baseline and/or of those that appeared at a subsequent visit)
4. Results not available/subject unevaluable (i.e., visit and/or assessment of clinical symptoms and physical findings of fungal disease was not performed at any time point)
5. No attributable signs and symptoms at Screening (i.e., no clinical symptoms or physical findings of fungal disease present at Baseline)

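### SAP Table 5 counts SGRQ stability as CPA Clinical Response, where protocol Table 16 requires a fall of at least 4 points, and neither document states or justifies the change

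*SAP*

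**What the plan says.** Protocol section 18.4.2.1, Table 16, CPA row: Clinical Response is "defined as a decrease in the St. George's Respiratory Questionnaire (SGRQ) score by" at least 4 points. The row then sorts SGRQ outcomes into three bands: improvement (a fall of 4 or more), deterioration (a rise of 4 or more) and, between them, "Stability: Change in SGRQ between: increase by <4 to decrease by <4".

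SAP Table 5, CPA row, keeps the same three bands, but there Clinical Response is "defined as improvement or stability in the St. George's Respiratory Questionnaire (SGRQ) score".

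Two places could have explained the difference:

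- Protocol Appendix A, Amendment 3, has a list headed "Outcome definitions changed as follows". It covers EC and OPC, VVC and the EORTC-MSG table. It has no entry for CPA Clinical Response.
- The SAP document history for version 1.1 describes its Table 5 edits only as "Clarification around definitions used for Global, Clinical, and Mycological Response". It does not mention CPA, the SGRQ or stability, and gives no reason.

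Clinical Response is an overall secondary endpoint. SAP sections 3, 7, 7.1.1 and 7.2.1 report it by fungal disease, disease category, pathogen and reason for enrollment, and for all diseases pooled. CPA sits in the Aspergillus-syndromes category.

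**The concern.** The two current documents give one endpoint two responder definitions, and the difference runs one way. A subject whose score does not move, or worsens by just under 4 points, is outside the protocol's response category and inside the SAP's. A reader who takes the definition from the protocol will read the reported CPA rate as the share who improved by at least 4 points, when it may be the share who did not deteriorate.

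This matters more because the study is open-label and single-arm. There is no concurrent arm to which the same lenient rule would apply, so the responder definition carries the interpretation. Protocol section 18.4.3 also says that estimated response rates will be assessed relative to external data. The SAP's secondary-endpoint section does not repeat that plan and no external SGRQ comparator is named, so this is a supporting reason only.

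Subjects may also enter for intolerance, toxicity or because long-term IV therapy is not feasible. A CPA subject enrolled for such a reason could have unchanged symptoms throughout and still be counted as a clinical responder under the SAP.

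**Working it through.** The plan gives no SGRQ response rate, CPA sample size or SGRQ standard deviation, so there is no figure of its own to reproduce. The check is set inclusion, followed by illustrations under stated assumptions.

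**Step 1: direction (from the documents).** Let d be the change in SGRQ from baseline.

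- Protocol responder: d ≤ -4.
- SAP responder: d ≤ -4 or -4 < d < +4, that is, d < +4.
- Deterioration, in both documents: d ≥ +4.

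The three bands are exhaustive and do not overlap. Every protocol responder is therefore an SAP responder, and the SAP set is everyone who did not deteriorate. With the same subjects and denominator:

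SAP rate - protocol rate = (number stable) / N ≥ 0, with equality only if nobody is stable.

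**Step 2: effect of one stable subject.**

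- CPA row: 1/5 = 20 points at N = 5 (the smallest group for which the SAP gives a CI), 1/10 = 10 points at N = 10, 1/20 = 5 points at N = 20.
- All diseases pooled, at planned enrolment: 1/220 = 0.45 points, or 1/242 = 0.41 points with the extra 10%. The actual ITT count may differ, and the Myco-ITT and PP denominators will be no larger than the ITT one.

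**Step 3: possible size in the CPA row (assumed distribution).** Take d as normal with mean μ and SD σ. The protocol rate is Φ((-4 - μ)/σ) and the SAP rate is Φ((4 - μ)/σ). For example, μ = 0 and σ = 8 give Φ(-0.5) = 30.9% and Φ(0.5) = 69.1%.

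| Assumed mean | Assumed SD | Protocol rule | SAP rule | Added (points) |
|---|---|---|---|---|
| -8 | 8 | 69.1% | 93.3% | 24.2 |
| -8 | 20 | 57.9% | 72.6% | 14.6 |
| -4 | 8 | 50.0% | 84.1% | 34.1 |
| 0 | 8 | 30.9% | 69.1% | 38.3 |
| 0 | 20 | 42.1% | 57.9% | 15.9 |
| +4 | 8 | 15.9% | 50.0% | 34.1 |
| +4 | 20 | 34.5% | 50.0% | 15.5 |

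Differences are taken before rounding. For a given SD the gap is largest at a mean of 0, so the mean has to be varied as well as the SD. Over the whole grid the addition runs from 14.6 to 38.3 points.

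**Step 4: possible size in the pooled rate (assumed 5 to 30 CPA subjects among 220).** Low end: 5/220 × 14.6 = 0.33 points. High end: 30/220 × 38.3 = 5.2 points.

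**Step 5: how a small table would look (invented split).** Ten CPA subjects with 3 improved, 4 stable and 3 worse give 3/10 = 30% (Clopper-Pearson 6.7% to 65.2%) under the protocol, and 7/10 = 70% (34.8% to 93.3%) under the SAP.

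**The case against.** The strongest objection is that the SAP sentence may not determine the reported rate. Both documents leave further detail of the DRC's criteria to a Charter that is not among them, and protocol section 18.4.2 points to Table 16. If the DRC adjudicated under Table 16, the SAP wording changed no adjudicated outcome. This stands, and it is why the size is conditional. It does not remove the conflict: a Charter that adds detail does not reconcile two different base definitions.

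It can also be said that stability is a reasonable aim in CPA, and that a reasoned, documented change reported beside the protocol-defined rate would cure the problem too. Both points are fair. What is missing is the reasoning and the documentation. In the same SAP row, Global Response credits stability only for "those that achieved stable disease after entering the study with a rapidly progressing condition"; the SGRQ rule carries no such condition.

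Third, the three bands are already in the SAP, and table shells are kept outside it, so a breakdown by band may already be planned. That is possible, but the SAP does not commit to one.

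A reader might go further than the documents allow in four ways:

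- **That the primary endpoint was loosened.** The CPA Global Response wording is the same in both documents and has no SGRQ cut-off.
- **That the Investigator's rate is inflated too.** SAP section 7.2.3 gives the Investigator a separate five-category scale, starting from "Resolution of all attributable clinical symptoms and physical findings", with no SGRQ rule.
- **That the SAP contradicts its own Table 6, where a stable outcome is a failure.** Table 6 classifies Global Response, not Clinical Response, and SAP section 7.1 says: "The analysis criteria will be based on EORTC-MSG Consensus Criteria for all diseases except ABPA, CPA and VVC". The comparison does not carry over.
- **That version 1.1 introduced the change.** The history entry is too general to show whether version 1.0 already had this wording.

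**Conclusion.** The discrepancy is certain and so is its direction. Where the SAP wording is applied, the DRC-assessed CPA Clinical Response rate is equal to or higher than the protocol-defined rate, by exactly the stable share. The same holds for every DRC-assessed clinical response table that contains CPA subjects: CPA, Aspergillus syndromes, by pathogen, by reason for enrollment, and all diseases pooled.

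The size is not known. About 15 to 38 points in the CPA row rests on assumed normal changes with mean -8 to +4 and SD 8 to 20. About 0.3 to 5.2 points in the pooled rate rests in addition on an assumed 5 to 30 CPA subjects among 220. Whether any reported rate actually moved depends on which wording the DRC applied, and the documents do not settle that.

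This concerns one secondary endpoint for one disease in an exploratory study. It does not undermine the primary analysis. It should still be corrected, because as written the SAP reports a non-deterioration rate under the name the protocol gives to an improvement rate.

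**What to change.** 1. In SAP Table 5, restore CPA Clinical Response as an SGRQ decrease of at least 4 points. Apply it to all DRC-assessed clinical response tables that include CPA subjects, including those by pathogen and by reason for enrollment.
2. Commit to tabulating improvement, stability and deterioration for CPA subjects at each SGRQ visit.
3. Show any rate that combines improvement and stability only as a labelled supportive analysis, with the departure from protocol Table 16 stated and justified.
4. State in the SAP that the Investigator's Clinical Response uses the scale in section 7.2.3.
5. Check the DRC Charter against Table 16 and align it if needed.

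The cost is SAP wording, one response definition and one three-row table per visit. No new data are needed: protocol section 14.2.7 already schedules the SGRQ at Screening or Baseline, Day 90, Day 180, every 3 months on therapy after that, EOT and the 6-Week FU. If the DRC used the SAP wording, the CPA clinical adjudications would have to be re-read. The downside for the sponsor is a less favourable CPA secondary rate and slightly lower pooled clinical response rates.

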Chronic Pulmonary Aspergillosis (CPA)	
CPA diagnosed according to the European Respiratory Society 2016 guideline, including:
 
 Thoracic imaging (preferably by CT) consistent with CPA, such as: 
 Aspergilloma Chronic cavitary pulmonary aspergillosis Subacute invasive aspergillosis (1-3 months) 
AND
 
 Direct evidence of Aspergillus infection or an immunological response to Aspergillus spp. 
 Percutaneous biopsy showing fungal hyphae on microscopy or growing Aspergillus spp. from a pulmonary lesion, OR Respiratory samples showing hyphae consistent with Aspergillus and/or growing Aspergillus spp. and/or with a positive Aspergillus PCR 
AND
 
 High Aspergillus IgG in a serum sample 
AND
 
 Active mycobacterial infection ruled out Disease present for at least 3 months Disease requires antifungal treatment for CPA, in the opinion of the Investigator 	
For CPA, refractoriness is defined as meeting any of the following criteria:
 
 Suboptimal clinical response (per the Investigator's judgment) of CPA signs and symptoms after receipt of SOC antifungal therapy for at least 6 weeks, including: 
 Significant hemoptysis Weight loss Persistent fatigue Productive cough Presence of new or worsened CPA signs and symptoms (expected to respond to antifungal treatment) while receiving SOC antifungal therapy for at least 6 weeks Persistence of azole-resistant Aspergillus spp. positive sputum or BAL cultures after at least 3 months of SOC antifungal therapy Radiologic evidence of lack of improvement, such as: 
 New cavities Increased peri-cavity infiltrates New fungal ball

Eligibility Criteria		
Fungal Disease	Diagnostic Criteria	Refractoriness/Resistance/Intolerance ^a /Toxicity ^b /Relapse ^c Criteria

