## 7. EFFICACY

The primary efficacy and secondary efficacy endpoints will be performed on the ITT, Myco-ITT and PP populations. The ITT analyses will be considered primary and the Myco-ITT and PP analysis will be considered supportive of the primary analyses on the ITT population.

The primary efficacy endpoint of the study is the percentage of subjects who achieve Global Response at TOC for VVC (Day 17), CMC (EOT or Day 84), CPA (EOT or Day 90) and ABPA (EOT or Day 90) (whichever comes first) and at EOT for all other diseases, as determined by the DRC. The primary efficacy endpoint will also be summarized by disease category and reason for enrollment separately. Secondary efficacy endpoints include the percentage of subjects who achieve Global Response, Clinical Response and Mycological Response by pathogen, fungal disease, disease category, and reason for enrollment at several time points as assessed by the DRC and by the Investigator. The following enrollment categories, as determined by the DRC unless stated otherwise, will be utilized: Refractory, Intolerant, Resistant (includes step-down cases), Toxicities, Relapse, Step-Down (as determined by PI). Each subject's enrollment reason will be validated by the DRC. The percentage of subjects with a recurrence, ACM and time to death will also be assessed.

Efficacy outcomes will be based on definitions captured in [Table 5](#) and [Table 6](#). Criteria for the DRC assessment of response will be further detailed in the DRC Charter. Criteria for the Investigator is outlined in [Section 7.2](#).

Efficacy evaluations will consist of clinical evaluations of the signs and symptoms of infection, mycological testing (including, but not limited to, fungal culture, KOH and other fungal stains, and T2 testing), imaging (e.g., CT, MRI, X-Ray or ultrasound) and serological testing (including, among others,  $\beta$ -D-glucan levels, GM and fungal antibody titers) as applicable for each fungal disease. Additional procedures (esophagoscopy, spirometry, St. George's Respiratory Questionnaire [SGRQ], 6-Minute Walk Test and Medical Research Council [MRC] Dyspnea Scale) will be conducted for selected fungal diseases.

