	For VVC: TOC (Day 17) (Day 17, 25-Day FU [Day 32], 35-Day FU [Day 42])	For VVC: Global Response = Clinical Success , defined as at least 50% reduction from baseline in total composite score, without use of additional antifungal	For VVC: Global Response (as defined) Clinical Response : 
 
• Clinical Cure, defined as complete resolution of all signs and symptoms (VSS = 0) without use of additional antifungal (Reference FDA guidelines 2016); OR
 
• Resolved VVC infection (VSS < 3)
 
 Mycological Response : 
 
• = mycological eradication of the baseline pathogen OR
 
• Presumed eradication of the baseline pathogen Symptom resolution at FU (clinical cure, resolved infection, clinical success)
 
 Responder outcome (clinical cure and mycological eradication)

Fungal disease	Primary time point (Secondary time points)	Primary Outcome Definition	Secondary Outcome Definitions (disease-specific outcome definitions, if not previously defined) a, e
Disseminated/invasive dimorphic fungi: 
 
• Coccidioidomycosis
 
• Histoplasmosis
 
• Blastomycosis
 
	EOT (EOT, Day 42, Day 84, 6-Week FU)	Global Response = Global Response based on MSG-EORTC outcome response definitions b	Global Response (as defined) Clinical Response (including radiological outcome) and Mycological Response Clinical and Mycological Responses based on MSG-EORTC outcome response definitions b

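### The secondary CPA Mycological Response can be met by a sputum culture that was already negative at entry

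*SAP*

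**What the plan says.** **Response rule.** The CPA row of SAP Table 5, in the column for secondary outcomes, makes a subject a mycological responder on a fall in Aspergillus IgG of at least 20% "AND/OR negative sputum culture for" Aspergillus. Protocol Table 16 has the same rule. Neither table asks what the culture showed at Screening or Baseline.

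**Entry rule.** Protocol Table 5 (Section 11.1) requires compatible imaging, high Aspergillus IgG, and one of two kinds of direct evidence:

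- a "Percutaneous biopsy showing fungal hyphae on microscopy or growing" Aspergillus from a lung lesion; or
- "Respiratory samples showing hyphae consistent with" Aspergillus, with growth as a further option, "and/or with a positive" Aspergillus PCR.

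Culture growth is one route among several.

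**Refractoriness.** For CPA, "refractoriness is defined as meeting any of the following criteria". One criterion is a suboptimal response "of CPA signs and symptoms after receipt of SOC antifungal therapy for at least 6 weeks". Persistently positive azole-resistant sputum or BAL cultures are another, and are not needed if a different criterion is met.

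**Population.** SAP Section 7 states: "The ITT analyses will be considered primary and the Myco-ITT and PP analysis will be considered supportive". ITT membership needs enrolment and one dose.

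**The concern.** The two limbs of the rule differ in kind. The IgG limb measures change from baseline. The culture limb records a state at one visit. Joined by and/or, the culture limb alone is enough, so a subject can respond without anything having changed since the first dose.

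Neighbouring definitions handle this differently. The VVC row speaks of "Presumed eradication of the baseline pathogen". The ABPA row asks for clearance of radiographic lesions only where lesions existed before treatment. CPA radiology has a precedence rule under which any deterioration overrides improvement. CPA mycology has no such rule, so a negative culture outranks a rising IgG.

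At stake is a secondary endpoint that will be reported with 95% confidence intervals. In a single-arm study whose estimated rates will be set against external data (Protocol Section 18.4.3), a response rule that needs no change makes the CPA mycological rate hard to interpret.

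**Working it through.** The plan gives no CPA sample size, baseline culture rate or expected response rate, so there is no figure of its own to reproduce. The check is one of logic, followed by an illustration.

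**Step 1. Can a culture-negative subject enter?** Yes. Biopsy microscopy, hyphae in a respiratory sample, or a positive PCR each satisfies the direct-evidence requirement without culture growth, and refractoriness can be met on symptoms or imaging.

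**Step 2. Is that subject then a responder without change?**

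| Item | Screening/Baseline | Day 90 |
|---|---|---|
| Direct evidence | PCR positive | not needed for the rule |
| Sputum culture | negative | negative |
| Aspergillus IgG | high | unchanged or higher |

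The IgG limb fails and the culture limb is met. Result as written: responder.

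**Step 3. Does another provision stop this?**

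- *Myco-ITT* (SAP Section 3.2) needs a confirmed pathogen and the necessary tests. A biopsy- or PCR-confirmed subject can qualify with a negative sputum culture.
- *Investigator scale, category 6* (SAP Section 7.2.3) sets apart subjects with no mycological evidence at Screening. It belongs to the generic Investigator scale, is not linked to the CPA row, and need not capture someone positive by biopsy or PCR.
- *Footnote e to SAP Table 5* gives the DRC discretion where the MSG-EORTC criteria do not fully apply. CPA is outside those criteria (SAP Section 7.1) and has its own definition.

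None of these closes the gap for the DRC-assessed endpoint.

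**Step 4. Size.** Let

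- q = share of CPA subjects who are culture-negative at entry and stay negative;
- p = proportion of those who reach the IgG criterion;
- r = response rate in the remaining subjects.

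Rate as written = q + (1 − q)r. Rate with a conversion requirement = qp + (1 − q)r. Excess = q(1 − p), whatever r is.

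With p = 0.30 (assumed):

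| q (assumed) | q(1 − p) | Excess |
|---|---|---|
| 0.20 | 0.20 × 0.70 | 14 points |
| 0.40 | 0.40 × 0.70 | 28 points |
| 0.60 | 0.60 × 0.70 | 42 points |

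Other inputs move this widely. With p = 0.20, the excess is 0.10 × 0.80 = 8 points at q = 0.10 and 0.75 × 0.80 = 60 points at q = 0.75.

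On the interval scale, assume n = 20, q = 0.50 and p = r = 0.20. The rate as written is 0.50 + 0.50 × 0.20 = 0.60, or 12/20 (Clopper-Pearson 95% CI 36.1% to 80.9%). With conversion required it is 0.20, or 4/20 (5.7% to 43.7%).

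The arithmetic takes every culture-negative entrant to have IgG at both time points.

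**The case against.** **The primary endpoint is not touched directly.** A reader might infer that the culture limb supplies the mycological part of the primary CPA Global Response. The documents do not say so. Global Response has its own column and rests on the DRC judging that the disease improved on clinical, radiological and mycological grounds, or became stable after rapid progression. A culture that is negative twice is not improvement in that sense. Any influence would run through DRC judgement. This objection stands.

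**The Charter may settle it.** Protocol Section 18.4.4 says the DRC Charter holds detailed criteria for baseline and outcome. It may contain a baseline condition. What can be said is that the protocol and SAP do not state one, not that adjudicated results are inflated. This also stands, although a condition that decides who is a responder belongs in the SAP.

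**The size is assumed.** Neither q nor p is in the documents. A reader might also infer that clearance by earlier standard therapy is being credited to ibrexafungerp. The prior-treatment criterion makes that possible, but nothing shows that it happens.

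**A narrow repair would do harm.** Accepting only a positive baseline sputum culture would deny the culture limb to subjects whose growth came from BAL or biopsy, which entry allows. CPA serology follows a recommended schedule (Protocol Table 13), so some follow-up IgG may be missing. The repair has to deal with both.

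**The endpoint is minor.** It is one secondary endpoint in one disease of an exploratory study. That limits the weight of the point but does not make the definition correct.

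**Conclusion.** The point holds for the secondary, DRC-assessed CPA Mycological Response. As written, a subject culture-negative at entry and at the time point is a responder even if IgG is flat or rising, and no provision in the protocol or SAP prevents this. The direction is certain: adding a baseline condition to the culture limb cannot raise the rate. The size is not known. It is q(1 − p), or 14 to 42 points for q from 0.20 to 0.60 with p = 0.30, all assumed. The change should be made, but it does not undermine the primary analysis. The conclusion is subject to the DRC Charter, which was not among the documents.

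**What to change.** In the CPA row of SAP Table 5 and Protocol Table 16:

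- count the culture limb only for subjects with a positive Aspergillus culture from a respiratory sample (sputum or BAL) or lung biopsy at Screening/Baseline and a negative culture at the time point;
- judge all other subjects on the IgG criterion (fall of at least 20%), and as not evaluable if baseline or follow-up IgG is missing;
- report the number of CPA subjects who were culture-positive at baseline.

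If the Charter already contains such a condition, state it in the SAP.

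The SAP describes DRC adjudication in the past tense. If it is complete under the current wording, leave it as it is and present the conversion-based rate beside it, derived from the collected culture and IgG data. That avoids re-adjudication.

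**Cost.** No new data collection: the protocol schedules mycological samples at Screening and/or Baseline for all non-VVC subjects (Section 14.2.2.2), requires high IgG at CPA entry, and schedules IgG at Day 90 and Day 180 (Section 14.2.4). The downside is a lower reported CPA mycological rate and possibly a few more not-evaluable subjects.
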